6.8 Examination of Subgroups

As exploratory analyses, subgroup analyses will be conducted for selected endpoints.

Subgroup analyses to be conducted are:

- Age (<65, \geq 65 years old)
- Age (<75, \geq 75 years old)
- Sex (female, male)
- Race (white, non-white)
- ECOG performance score at baseline (0, 1-2)
- Bellmunt risk score (0-1, \geq 2) ([Bellmunt 2010](#))
- Baseline weight (\leq 100, $>$ 100 kg)
- Primary tumor sites (upper tract, bladder/other)
- Liver metastasis (yes, no)
- Number of prior systemic therapy in locally advanced or metastatic setting (1-2, \geq 3)

- Best response to prior CPI (responder, non-responder)
- PD-L1 CPS ($<10, \geq 10$)

A subgroup analysis may not be performed if the number of subjects in the subgroup is not sufficiently large (i.e., $<10\%$ of the full analysis set for a given cohort). At the time of the primary analysis of Cohort 1, subgroup analysis will be performed for Cohort 1 only, without including Cohort 2 subjects.

6.9 Covariates

No adjustment for covariates is planned in the analyses.

6.10 Timing of Analyses

The primary analysis of Cohort 1 (platinum-treated subjects) will be conducted when enrollment is completed in Cohort 1 and all subjects in this cohort have been followed for at least 6 months, discontinued from study, or had 30 days safety follow up after PD, whichever comes first.

Analysis for Cohort 2 will occur at 4 timepoints;

- 1) at the time of the primary analysis of Cohort 1,
- 2) when approximately 50 subjects in Cohort 2 have had the opportunity to be followed for approximately 8 months from the first dose of enfortumab vedotin,
- 3) when approximately 70 subjects in Cohort 2 have had the opportunity to be followed for approximately 8 months from the first dose of enfortumab vedotin, and
- 4) when all subjects in Cohort 2 have had the opportunity to be followed for approximately 8 months from the first dose of enfortumab vedotin.

Additional cutoff dates may be defined and corresponding database locks may occur to allow for more precise estimates of time-to-event endpoints.

7 PLANNED ANALYSES

7.1 Disposition

Subject disposition will be summarized for all enrolled subjects with descriptive statistics. Subjects who discontinue study treatment and subjects who withdraw from the study will be summarized along with the reason for discontinuation or withdrawal.

The number of subjects who signed informed consent, number of screen failures, and the reason for screen fail will be summarized for all screened subjects. The number of subjects enrolled at each site will be summarized.

7.2 Demographic and Baseline Characteristics

Demographics and baseline characteristics, including age at consent, sex, ethnicity, race, baseline height, weight, body mass index, ECOG performance status, estimated creatinine clearance, hemoglobin A1c, smoking status, and Bellmunt risk factors will be listed and summarized with descriptive statistics for the full analysis set.

Disease specific characteristics, including time from diagnosis of locally advanced/metastatic disease to enrollment, histology, current extent of disease, disease stage, primary tumor location, and metastases sites will be listed and summarized for the full analysis set.

Summary of prior cancer-related therapies, including number of prior therapies, therapy type, setting of prior therapies, best response to prior therapies, time from most recent prior therapy to first dose of study drug, and prior cystectomy and nephrectomy, will be presented for the full analysis set.

In addition, the pre-existing conditions that are ongoing at baseline will be summarized.

7.3 Protocol Deviations

Important protocol deviations are a subset of protocol deviations that may represent a divergence from the protocol that could have a significant effect on the integrity of the study data, or on the subject's rights, safety, or welfare. Important protocol deviations also include exemptions to the study inclusion/exclusion criteria and will be summarized by category. A list of subjects with important protocol deviations will be presented.

7.4 Treatment Administration

Treatment administration will be summarized for the safety analysis set. Summary statistics for duration of treatment (weeks), number of cycles, and the number and percentage of subjects who were treated at each cycle will be presented. In addition, number of infusions per subject, cumulative dose administered, absolute dose intensity (ADI), and relative dose intensity (RDI) will be described. The number and percentage of subjects whose dose was ever modified will be summarized.

Duration of treatment is defined as time from the first study dose to the earliest of the following:

- Day 28 of the last treatment cycle
- Date of death
- Analysis cutoff date if the subject is still on treatment at the time of the analysis
- Start of subsequent anticancer therapy

Intended dose intensity (IDI) is defined as the intended dose of study drug per unit of time according to the protocol (i.e., 3.75 mg/kg/4-wk cycle).

ADI is defined as the actual dose of study drug per unit of time that a subject received over the entire treatment period. For the purpose of calculating ADI, treatment period is defined as time from the first dose of study drug to Day 28 of the last treatment cycle, regardless if death occurs before the end of the cycle.

RDI is defined as the ADI over the IDI (i.e., $RDI = ADI/IDI * 100\%$).

7.5 Efficacy Analyses

The primary analysis of efficacy endpoints will be performed using the full analysis set. Sensitivity analysis of the primary efficacy endpoint will be presented using the efficacy evaluable set.

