9.3.1.7 Analysis Sets

The full analysis set will include all patients who are enrolled and receive any amount of enfortumab vedotin in the study. A patient is considered enrolled if he/she has met all criteria for participation in the study and has Seagen approval as documented in the eCRF. The full analysis set will be used as the primary dataset for efficacy analysis. Patient demographics and baseline disease characteristics will be summarized based on the full analysis set.

The safety analysis set will include all patients who receive any amount of enfortumab vedotin. The safety analysis set will be used for all safety analyses.

The efficacy evaluable set will include all patients in the full analysis set who started treatment with enfortumab vedotin at least 8 months before the analysis data cutoff. The efficacy evaluable set will be used for the additional analyses of efficacy endpoints at the time of the interim analyses of Cohort 2 to allow adequate follow up for a stable estimate of ORR and DOR.

The PK analysis set will include all patients who received enfortumab vedotin and from whom at least one blood sample was collected and assayed for enfortumab vedotin, MMAE, or TAb concentration. Corresponding records of the time of dosing and sample collection must also be available for all enfortumab vedotin, MMAE, and TAb concentration data. The PK analysis set will be used for PK analyses.

Additional analysis sets of patients may be defined in the SAP.

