5.3 Efficacy Evaluable Set

The efficacy evaluable set will include all subjects in the full analysis set who started treatment with enfortumab vedotin at least 8 months before the analysis data cutoff. The efficacy evaluable set will be used for the additional analyses of efficacy endpoints at the

time of the Cohort 2 interim analyses to allow adequate follow up for a stable estimate of ORR and DOR.

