6.5 Handling of Dropouts and Missing Data

Missing data will not be imputed unless otherwise specified.

For time-to-event endpoints (e.g., duration of response, PFS, and OS), subjects who have no specified event will be censored as specified for each respective endpoint in Section 7.5.

Subjects who do not have at least two (initial response and confirmation scan) post-baseline response assessments will be counted as non-responders for the analysis of primary endpoint.

Missing AE dates will be imputed for the purpose of calculating duration of events and treatment-emergent status (see [Appendix A](#) for imputation details and [Appendix B](#) for treatment-emergent definition).

Missing prior therapy dates will be imputed for the purpose of calculating the time from prior therapy to first dose of study drug (see [Appendix C](#) for details).

Missing subsequent anticancer therapy start date will be imputed for the purpose of deriving the time-to-event endpoints as applicable (see [Appendix D](#) for details).

Unless otherwise specified, if the numeric value of a laboratory test is not available because it is below the lower limit of quantification (LLOQ), the result will be analyzed as equal to the LLOQ when a numeric value is required (e.g., calculating the mean) and be listed as “< LLOQ” in the listings.

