7.5.4 Disease Control Rate at Week 16 (DCR₁₆)

DCR₁₆ per IRF is defined as the proportion of subjects with CR, PR, or SD at Week 16 (± 1 week) based on IRF assessment. Responses do not need to be confirmed for the purpose of determining DCR₁₆. Subjects whose disease status cannot be assessed or have a missing

assessment at Week 16 will be considered not having disease control at Week 16. The only exception is for subjects who have a CR, PR, or SD at the visits subsequent to Week 16; these subjects will be considered to have disease control at Week 16 although the Week 16 assessment is missing or not evaluable.

DCR₁₆ per IRF will be summarized for the full analysis set. The exact two-sided 95% CI will be calculated.

DCR₁₆ per investigator will be analyzed in the same way as the DCR₁₆ per IRF.

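### Does the SAP leave it unclear which endpoints and interim looks use the efficacy evaluable set, so that immature Week 16 disease control is reported without a companion?

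*SAP*

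**What the plan says.** The efficacy evaluable set consists of full-analysis-set patients first dosed at least 8 months before the data cutoff. Its use is described in several places.

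- SAP section 5.3: "The efficacy evaluable set will be used for the additional analyses of efficacy endpoints at the" time of the Cohort 2 interims, with a stable estimate of ORR and DOR as the stated aim.
- Protocol section 9.3.1.7: "The efficacy evaluable set will be used for the additional analyses of efficacy endpoints at the time of the interim analyses of Cohort 2". The Protocol synopsis and section 9.3.5 agree.
- SAP section 7.5, after making the full analysis set primary for efficacy: "Sensitivity analysis of the primary efficacy endpoint will be presented using the efficacy evaluable set". It gives no cohort or timepoint.

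For DCR16, SAP section 7.5.4 says that the rate "per IRF will be summarized for the full analysis set". Patients who cannot be assessed or who lack an "assessment at Week 16 will be considered not having disease control at Week 16", unless a later visit shows CR, PR or SD. For the primary endpoint, SAP section 6.5 says that patients without two "post-baseline response assessments will be counted as non-responders for the analysis of primary endpoint".

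On timing, SAP section 6.10 runs the Cohort 1 primary analysis once "all subjects in this cohort have been followed for at least 6 months, discontinued from study" or completed 30 days of safety follow-up after progression. The first of four Cohort 2 analyses is "at the time of the primary analysis of Cohort 1", with no minimum Cohort 2 follow-up. The second and third come when about 50 and about 70 Cohort 2 patients have had about 8 months of potential follow-up, and the fourth when all have.

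**The concern.** Read separately, SAP sections 5.3 and 7.5 give the evaluable set two scopes: all efficacy endpoints at the Cohort 2 interims, or the primary endpoint at an unstated time. Three consequences seem to follow.

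1. **DCR16.** The full analysis set has no minimum follow-up. A patient dosed less than about 16 weeks before an interim cutoff therefore counts as a failure by rule. If 7.5 is the whole instruction, no evaluable-set DCR16 accompanies that diluted figure.
2. **Cohort 1.** Taken literally, 7.5 also covers the Cohort 1 primary analysis. Follow-up there need only reach 6 months, so an 8-month set could drop recently treated patients.
3. **First Cohort 2 look.** Patients may have been treated so recently that the evaluable set is empty or nearly so. SAP section 6.1 also calls in general for combined-cohort results, which would carry the same immaturity.

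At stake is how interim estimates are read, and whether an evaluable-set DCR16 is prespecified or post hoc.

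**Working it through.** **The plan's own figures.** For n = 100, a null rate of 10% and one-sided 0.025, the smallest exact critical value is 17 responses (attained level 0.0206). Power is 97.9% at 25% and 80.8% at 20%, matching the stated 98% and 81%. Clopper-Pearson limits at 30% observed are 11.9–54.3% (6/20), 17.9–44.6% (15/50), 19.6–42.1% (21/70) and 21.2–40.0% (30/100), matching the SAP section 6.2 table. The concern affects none of these.

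**Dilution of interim DCR16 on the full analysis set.** From the documents: looks 2 and 3 occur when k = 50 or 70 patients have 8 months; Cohort 2 is capped at about 100; 16 weeks = 112/30.4375 = 3.68 months. Assumed, because the documents are silent: uniform accrual of r = 1 to 5 patients a month continuing to the cutoff or the cap, and a true DCR16 of 60%.

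- Treated: N = min(100, k + 8r).
- Under 16 weeks: u = r × max(0, min(8, (100 − k)/r) − (8 − 3.68)).
- Expected full-set DCR16 = 60% × (N − u)/N.

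Example, k = 50 and r = 3: N = 50 + 24 = 74; u = 3 × 3.68 = 11.04; 60% × 62.96/74 = 51.0%.

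| r per month | Look 2: N | u (share) | DCR16 | Look 3: N | u (share) | DCR16 |
|---|---|---|---|---|---|---|
| 1 | 58 | 3.7 (6.3%) | 56.2% | 78 | 3.7 (4.7%) | 57.2% |
| 2 | 66 | 7.4 (11.2%) | 53.3% | 86 | 7.4 (8.6%) | 54.9% |
| 3 | 74 | 11.0 (14.9%) | 51.0% | 94 | 11.0 (11.7%) | 53.0% |
| 4 | 82 | 14.7 (17.9%) | 49.2% | 100 | 12.7 (12.7%) | 52.4% |
| 5 | 90 | 18.4 (20.4%) | 47.7% | 100 | 8.4 (8.4%) | 55.0% |

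The shortfall is 3.8 to 12.3 points at look 2 and 2.8 to 7.6 at look 3. It scales with the assumed true rate. In the evaluable set it is zero, because 8 months is 8 × 30.4375 = 243.5 days, well past Week 16. At timepoint 4 every patient has had about 8 months, so it is zero in the full set too.

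**Evaluable set at look 1.** Take 20 treated patients (the SAP table's smallest row, assumed to be look 1) accrued uniformly over A months. The evaluable number is 20 × max(0, A − 8)/A: 0 for A up to 8, 2.2 at 9, 4.0 at 10, 6.7 at 12, 11.1 at 18 and 13.3 at 24. A nearly empty set is possible, but the documents do not show that it will occur.

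**The passages side by side.**

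- SAP section 3.2 lists DCR16, per IRF and per investigator, among the secondary endpoints. It is an efficacy endpoint, so SAP section 5.3 and Protocol section 9.3.5 cover it at the Cohort 2 interims.
- SAP section 7.5 names one evaluable-set analysis and does not exclude others. It can be read as one case of 5.3.
- SAP section 7.5.4 does not mention the evaluable set, so it is silent and not in conflict. Sections 7.5.1 and 7.5.2 likewise name only the full analysis set, which fits its role as the primary set.
- SAP section 9.2 suggests how the wording arose. Version 2 added the set as a sensitivity analysis of the primary endpoint. Version 3 redefined it for the interims and records no change to 7.5.
- Protocol section 9.3.2 requires the number of patients in each analysis set. Full set minus evaluable set is the number dosed under 8 months before cutoff.

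**The case for a change.** The strongest case for a change is procedural. SAP section 1 commits to every analysis specified, and section 6.1 treats any analysis not described as post hoc. On that view two scopes for one set matter: an evaluable-set DCR16 is prespecified under 5.3 but could be called post hoc by someone relying on 7.5, and 7.5 could be taken to require an 8-month analysis of Cohort 1. Aligning one sentence would cost little.

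Part of this stands. The two sections do differ in wording, and the interim full-set DCR16 is diluted by a non-trivial amount. But 5.3 is itself part of the SAP, so an evaluable-set DCR16 at a Cohort 2 interim is described and planned. Extending the set to Cohort 1 means setting aside the explicit limit to Cohort 2 interims in 5.3 and the protocol; even if someone ran it, the full analysis set would remain primary.

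The changes one might make add little. Rows counting patients under 12 and 16 weeks, and labels on combined-cohort interim results, are reporting preferences; the protocol makes the combined analysis optional. Restricting the set to the second and third looks would be narrower than the protocol, because Protocol section 9.3.10 lists the Cohort 1 timepoint among the interim analyses. It describes that look as a summary of available data, so a small evaluable set there is no departure from plan. Short follow-up also dilutes interim ORR on the full set, but both SAP sections already supply an evaluable-set ORR.

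**Conclusion.** No change to the plan is needed. The difference between SAP sections 5.3 and 7.5 is real but editorial, most likely a sentence left unrevised when the set was redefined. Reading the two together gives the intended analyses: the full analysis set as primary throughout, with the evaluable set beside it for efficacy endpoints, DCR16 included, at the Cohort 2 interims.

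The interim dilution of full-set DCR16 is about 3 to 12 percentage points at looks 2 and 3. That assumes a true rate of 60% and uniform accrual of 1 to 5 patients a month up to the cutoff or the cap. It shrinks to nothing if accrual stops well before the cutoff, and it is nil at timepoint 4. Look 1 could be affected more: under the same 60% and 20 patients accrued over 12 months, the full-set figure would be 60% × (1 − 3.68/12) = 41.6%. DCR16 is secondary and descriptive, its scoring rule is explicit and conservative, and no boundary or stopping rule uses it. Power, the significance level, the primary ORR and the final DCR16 are untouched.

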7.5.1 Primary Efficacy Endpoint - Objective Response Rate (ORR) per IRF

The primary endpoint of this study is the confirmed ORR per IRF. ORR is defined as the proportion of subjects whose best overall response is a confirmed CR or PR according to RECIST v1.1 (Eisenhauer 2009). Subjects who do not have at least two (initial response and confirmation scan) post-baseline response assessment will be considered non-responders.

The primary efficacy hypothesis is outlined in Section 6.2.

The ORR per IRF and its exact two-sided 95% CI will be calculated for the full analysis set.

In addition, the ORR per IRF will be summarized and presented graphically by the subgroups defined in Section 6.8.

The maximum percent reduction from baseline in the sum of diameters per IRF will be calculated for each subject and presented graphically with a waterfall plot.

Time to response per IRF will be calculated as the time from the first dose of study drug to the first documentation of objective response (CR or PR that is subsequently confirmed).

Time to response per IRF will be summarized for the responders only. Subgroup analysis of time to response will be performed for subjects who responded to the prior CPI therapy versus those who did not respond to the prior CPI therapy.

7.5.2 Objective Response Rate (ORR) per investigator

The ORR per investigator and its two-sided 95% exact CI will be calculated for the full analysis set.

The ORR per investigator in the subgroups will be presented graphically. The maximum percent reduction from baseline in sum of diameters per investigator will be calculated for each subject and presented graphically with a waterfall plot.

Time to response per investigator will be analyzed in the same way as the time to response per IRF.

7.5.2.1 Concordance between Investigator and IRF Assessment

A summary of the concordance between investigator and IRF assessment will be provided. The percent agreement will be calculated as the proportion of subjects whose best overall response per IRF match the best overall response per investigator.

Percent agreement = (Number of matched responders + Number of matched non-responders) / Total number of subjects assessed.

7.5.3 Duration of Response

DOF is defined as the time from the date of first documented response (CR or PR that is subsequently confirmed) to the date of first documented PD per RECIST v1.1 or death due to any cause, whichever comes first.

DOF will be censored as described below:

- Subjects who do not have PD and are still on study at the time of an analysis will be censored at the date of the last adequate response assessment documenting absence of PD
- Subjects who have started a new anticancer treatment (with the exception of palliative radiotherapy on a non-target lesion that is not progressing) prior to documentation of PD will be censored at the date of the last adequate response assessment prior to start of new treatment
- Subjects who discontinue from the study prior to documentation of PD will be censored at the date of the last adequate response assessment documenting absence of PD.

DOF per IRF will only be calculated for subjects achieving a confirmed CR or PR per IRF. DOF will be analyzed using Kaplan-Meier methodology and Kaplan-Meier plots will be provided. The median DOF and its two-sided 95% CI will be calculated. In addition, the DOF at 6 and 12 months will be summarized.

Sensitivity Analysis

The following sensitivity analysis will be performed for the DOF per IRF:

1. A sensitivity analysis to censor subjects who progressed or died after an extended loss to follow up (i.e., ≥ 2 consecutive missed response assessments) at the date of the last adequate response assessment prior to the missed visits.

DOF per investigator will be analyzed in the same way as the DOF per IRF.

7.5.4 Disease Control Rate at Week 16 (DCR₁₆)

DCR₁₆ per IRF is defined as the proportion of subjects with CR, PR, or SD at Week 16 (± 1 week) based on IRF assessment. Responses do not need to be confirmed for the purpose of determining DCR₁₆. Subjects whose disease status cannot be assessed or have a missing

assessment at Week 16 will be considered not having disease control at Week 16. The only exception is for subjects who have a CR, PR, or SD at the visits subsequent to Week 16; these subjects will be considered to have disease control at Week 16 although the Week 16 assessment is missing or not evaluable.

DCR₁₆ per IRF will be summarized for the full analysis set. The exact two-sided 95% CI will be calculated.

DCR₁₆ per investigator will be analyzed in the same way as the DCR₁₆ per IRF.

7.5.5 Progression-free Survival (PFS)

PFS is defined as the time from start of study treatment to first documentation of PD per RECIST v1.1 or death due to any cause, whichever comes first.

The same censoring rules as outlined in Section 7.5.3 for DOR will be applied to PFS. In addition, subjects who are not known to have died and do not have any post-baseline response assessment will be censored at the date of first dose.

PFS per IRF will be analyzed using Kaplan-Meier methodology and Kaplan-Meier plots will be provided. The median PFS and its two-sided 95% CI will be calculated. In addition, the 6- and 12-month PFS rates will be summarized.

Sensitivity Analysis

The following sensitivity analysis will be performed for the PFS per IRF:

1. A sensitivity analysis to censor subjects who progressed or died after an extended loss to follow up (i.e., ≥ 2 consecutive missed response assessments) at the date of the last adequate response assessment prior to the missed visits.

PFS per investigator will be analyzed in the same way as the PFS per IRF.

